4.4.5. Vital Signs and Physical Examination

The actual value and change from baseline to each on-study evaluation will be summarized for

vital signs, including blood pressure (systolic/diastolic), heart rate, body temperature, and respiratory rate and presented by treatment and dose and separately by concentration.

Vital sign measurements and all physical examination findings will be presented in by-subject data listings by cohort.

4.4.6. Auditory and Vestibular Assessments

Audiometric and vestibular tests will be performed at Screening, Baseline, Day 3, Day 10, Day 17, Day 24 and end of study (EOS).

4.4.6.1. Otoscopy

The number and percentage of subjects with otoscopic examination results (normal, abnormal, not done) for each ear will be summarized by visit, treatment and dose, and separately by concentration.

Otoscopic examination results for each ear and comments will be listed by cohort, subject and visit.

Use of hearing aid and regular/history of excessive noise exposure will be provided in by-subject data listings.

4.4.6.2. Pure Tone Audiometry and High Frequency Audiometry

Air conduction pure tone audiometry (PTA) will be conducted across the conventional range of frequencies (0.25, 0.5, 1, 2, 3, 4, 6, 8 kHz), as well as at high frequencies (10, 12, 14, 16 kHz). If there is a PTA threshold ≥ 15 decibels in hearing level (dB HL) for frequencies between 0.25 - 4 kHz, bone conduction will be performed at that frequency.

PTA/High Frequency Audiometry (HFA) threshold and change from baseline in PTA/HFA threshold for each ear at each frequency will be summarized descriptively (n, mean, SD, median, min, median, max) at each visit by treatment and dose, and separately by concentration.

Mean (\pm SD) changes from baseline in PTA/HFA threshold by dose will be plotted across all visits for each ear at each frequency.

For conventional frequencies (0.25 - 8 kHz) and HFA (10 - 16 kHz), the Significant Change Criteria as defined by American Speech-Language-Hearing Association (ASHA) and American Academy of Audiology (AAA) are when the thresholds worsen by the following criteria:

1. ≥ 20 dB change at any frequency,
2. ≥ 10 dB change at any 2 adjacent frequencies, or
3. loss of response at 3 consecutive frequencies where responses were obtained at baseline.

The number and percentage of patients with significant change relative to baseline across the conventional frequencies (yes, no) and significant change relative to baseline at the high frequencies (yes, no) will be summarized for each ear by visit, treatment and dose, and separately by concentration.

PTA and HFA data for each subject will be listed by cohort.

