- If an HFA ototoxic event occurs in 2 subjects receiving ELX-02 in any cohort, 6 subjects receiving ELX-02 and 3 subjects receiving placebo will be added to the current dose level, unless it is determined by the Sponsor and the AVDSMB, following a thorough medical review, that the study may resume. In this instance additional subjects will not need to be added.

- If an HFA ototoxic event occurs in  $\geq 3$  subjects receiving ELX-02 in any cohort, this will be considered a DLT and dose escalation to the next dose level will not be authorized. The previous dose level will be determined as the MTD.

If the criteria for stopping a dose has been met for an individual subject during a cohort, the study may be temporarily suspended immediately to allow for further medical evaluation with additional assessments of the propted event, as appropriate. If any subject/subjects meet dose stopping or significant change criteria, the sponsor, after discussion with PI, may pause the study for another careful review of data for all subjects; Study may be resumed for the remaining subjects after discussions between the sponsor and site, taking into consideration the safety surveillance of the discontinued participants, as well as, the dosed ones. If this occurs, the following process will be initiated:

- Subjects will continue their participation with the same dose in order to assure that all subjects receive their entire complement of nine doses per cohort.
- Subjects who have received the required number of injections for a dose on a dosing day prior to study suspension will continue with their next administration, regardless of the treatment day, in order to receive their total of 9 doses per cohort.
- Subjects who did not receive the required number of injections on a dosing day prior to study suspension will not need to repeat that dosing day, they will proceed to the next administration, regardless of the treatment day, in order to receive their total of

nine doses per cohort.

The discontinued subjects who met the significant change or dose stopping criteria will be followed for safety and surveillance audiology tests; the monitoring period will continue either until the resolution of the event, such time that it is determined that changes are permanent or the subject is lost to follow-up. The determination for permanency will be made by the AVDSMB and does not have a specified time frame.

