### Handling Subject Withdrawal

If a subject's participation in the study is prematurely terminated for any reason or fails to return for a scheduled visit, every effort should be made to determine the reason. This information will be recorded.

Upon withdrawal from the study, any time after dosing has taken place, all efforts should be made to invite the subject to complete the EOS visit.

If for any reason the subject does not agree to return to the CPU for the above visit, the reason and/or efforts made will be recorded.

If the subject withdraws from the study and also withdraws consent for disclosure of future information, no further evaluations should be performed, and no additional data should be collected. The Sponsor may retain and continue to use any data collected before such withdrawal of consent.

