1.2. Study Design

1.2.1. Synopsis of Study Design

This is a Phase 1, randomized, double-blind, placebo-controlled, third party open (i.e. pharmacist), multiple dose escalation study to evaluate the safety, tolerability and PK of SC administered ELX-02 in independent consecutive cohorts of healthy subjects.

The investigational drug, ELX-02, is formulated as a solution for SC injection, containing 200 mg/mL. The placebo control will consist of a SC injection of normal saline at matching volumes.

The study is designed to include at least 5 cohorts of 9 subjects each, including both males and females. Subjects will be randomized to receive multiple doses of ELX-02 or placebo at a ratio of 2:1 in each cohort; 6 subjects will receive ELX-02 and 3 will receive placebo for a total of up to 63 subjects. Study drug will be administered SC twice a week for 9 doses and dose levels planned in the protocol for each cohort are described below:

- Cohort 1: ELX-02 0.1 mg/kg or placebo
- Cohort 2: ELX-02 0.3 mg/kg or placebo
- Cohort 3: ELX-02 1.0 mg/kg or placebo
- Cohort 4: ELX-02 2.5 mg/kg or placebo
- Cohort 5: ELX-02 up to 2.5 mg/kg or placebo
- Cohort 6: ELX-02 2.5 to 5.0 mg/kg or placebo
- Cohort 7: ELX-02 up to 5.0 mg/kg or placebo

Dose escalation to the next cohort will not be performed until 14 days after the last subject's last dose in the previous cohort, to allow for detection of unanticipated delayed AEs.

The decision to proceed to a higher dose level will be following the recommendations of both the general Data Safety Monitoring Board (DSMB) and the Auditory and Vestibular Data Safety Monitoring Board (AVDSMB) based on the dose-escalation stopping rules. The DSMB and AVDSMB recommendation to proceed to a higher dose will be based on review of the blinded safety data, any available blinded PK data, and the results of audiologic tests and questionnaires. The next cohort will be dosed after the DSMB and AVDSMB have evaluated the available data and have recommended to escalate.

The principles of dose escalation, determination of dose limiting toxicity (DLT) and MTD, are detailed in Protocol Section 3.2.

Study duration will be approximately 12 weeks for each subject including a screening period of up to 6 weeks, treatment period of 4 weeks, and 2 weeks for final safety follow-up. Subjects will receive in-patient treatment in the Clinical Pharmacological Unit (CPU) for approximately 8 days throughout the treatment period.

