At the time this SAP was written, five doses have been investigated and two of the dose levels involved two different dilution schemes (different concentrations being injected), for a total of

seven cohorts. The final doses (ELX-02 injection solutions) administered in the study are summarized below:

- Cohort 1: ELX-02 0.1 mg/kg (50 mg/mL) or placebo
- Cohort 2: ELX-02 0.3 mg/kg (50 mg/mL) or placebo
- Cohort 3: ELX-02 1.0 mg/kg (100 mg/mL) or placebo
- Cohort 4: ELX-02 2.5 mg/kg (100 mg/mL) or placebo
- Cohort 5: ELX-02 1.0 mg/kg (50 mg/mL) or placebo
- Cohort 6: ELX-02 2.5 mg/kg (50 mg/mL) or placebo
- Cohort 7: ELX-02 5.0 mg/kg (50 mg/mL) or placebo.

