3. GENERAL STATISTICAL METHODS

3.1. Sample Size Justification

No formal sample size estimations were performed. The planned sample size of 9 subjects per dose group with a total of up to 63 subjects was considered sufficient to address the safety, tolerability and PK objectives of this study.

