3.11. Visit Windows

It is expected that all visits should occur according to the protocol schedule. All data will be tabulated per the nominal visit as recorded in the eCRF even if the assessment is outside of the visit window. In data listings, the relative day of all dates will be presented (see [Section 3.2](#)).

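### Audiometry is summarised only by nominal visit on observed cases, so if affected subjects stop being tested, mean hearing change and ASHA percentages can fall at Days 10-24 without recovery

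*SAP*

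**What the plan says.** SAP 4.4.6 names the test occasions: screening, baseline, Days 3, 10, 17 and 24, and EOS. Under SAP 4.4.6.2, "PTA/High Frequency Audiometry (HFA) threshold and change from baseline in PTA/HFA threshold for each ear at each frequency will be summarized descriptively" at each visit, mean change is plotted across visits, and the count and percentage meeting the ASHA criteria are given per ear and per visit. Each subject's PTA and HFA data are listed.

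SAP 3.10 makes no substitution for missing values. SAP 3.11 sets the row: "All data will be tabulated per the nominal visit as recorded in the eCRF even if the assessment is outside of the visit window".

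Protocol 3.2 provides for people who stop dosing: "The discontinued subjects who met the significant change or dose stopping criteria will be followed for safety and surveillance audiology tests". That surveillance has no fixed schedule and no specified end. For any withdrawal after dosing, Protocol 7.1 (Handling Subject Withdrawal) says "all efforts should be made to invite the subject to complete the EOS visit", and the EOS visit includes audiometry.

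For laboratory data, SAP 4.4.4 adds shift tables from baseline to worst and to last value, with unscheduled visits included. There is no audiometry counterpart.

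**The concern.** Hearing is a central safety question for an aminoglycoside derivative, and this trial has a separate auditory board. A by-visit, observed-case summary describes whoever was tested at that visit. If a person is discontinued because hearing worsened and is not tested at the next scheduled visits, the reason for absence is the outcome being summarised. The later rows then lean towards unaffected subjects, and a mean plot can show a rise followed by a return to zero when no ear has improved.

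At EOS there is a second problem. A withdrawn subject may be absent, or may attend early and be pooled with subjects tested after all nine doses. The SAP does not tell the two kinds of EOS audiogram apart. At stake is how the study report describes the size, persistence and reversibility of hearing change by dose.

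**Working it through.** **Column sizes.** The only design figure in the plan is a count: "6 subjects will receive ELX-02 and 3 will receive placebo for a total of up to 63 subjects". It reproduces: 7 cohorts × 9 = 63, with 7 × 6 = 42 active and 7 × 3 = 21 placebo. SAP 3.1 adds that "No formal sample size estimations were performed", so there is no planned SD or event rate to work from. SAP 1.2.1 also says that "five doses have been investigated and two of the dose levels involved two different dilution schemes". Active subjects per dose column are therefore 6 at 0.1, 0.3 and 5.0 mg/kg and 2 × 6 = 12 at 1.0 and 2.5 mg/kg (6 + 6 + 6 + 12 + 12 = 42). The by-concentration tables have 6 per column.

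**Doses before each test.** Dosing is on Days 1, 4, 8, 11, 15, 18, 22, 25 and 29. Doses received before the Day 3, 10, 17, 24 and EOS tests are 1, 3, 5, 7 and 9.

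**Assumed shift.** The documents give no shift size. I take S = 20 to 40 dB, with 30 dB as the worked case. For reference, 20 dB is the single-frequency ASHA limit, and an HFA ototoxic event is more than 25 dB averaged over three consecutive frequencies.

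**Formula.** Let k of n active subjects have a lasting shift S, and let the others average m.
- Row where the shift is found: [kS + (n − k)m] / n
- Later rows, if the k are not tested: m
- Apparent fall: k(S − m)/n, which is kS/n when m = 0

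| n | k | S (dB) | Mean when found | Later rows |
|---|---|---|---|---|
| 6 | 1 | 20 | 3.3 | 0 (n=5) |
| 6 | 1 | 30 | 5.0 | 0 (n=5) |
| 6 | 1 | 40 | 6.7 | 0 (n=5) |
| 6 | 2 | 30 | 10.0 | 0 (n=4) |
| 12 | 1 | 20 | 1.7 | 0 (n=11) |
| 12 | 1 | 30 | 2.5 | 0 (n=11) |
| 12 | 1 | 40 | 3.3 | 0 (n=11) |

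The ASHA criteria can also be met by 10 dB at two adjacent frequencies. At each of those, one such subject moves the mean by 10/6 = 1.7 dB or 10/12 = 0.8 dB.

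**EOS.** If the affected subject (S = 30, n = 6) attends with the shift unchanged, the EOS mean is 30/6 = 5.0 dB again. If that subject was also replaced, it is 30/7 = 4.3 dB. If the subject does not attend and was not replaced, it is 0 dB (n=5). A subject found at Day 10 and not dosed again would bring an EOS value taken after 3 doses into a row otherwise taken after 9.

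**Percentages.** Suppose two of six are first affected at Days 10 and 17 and each is untested afterwards. The rows read 1/6 (17%), 1/5 (20%) and 0/4 (0%) at Days 10, 17 and 24. The ever-affected figure is 2/6 (33%), and no planned audiometry table shows it.

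**Replacement.** SAP 3.9 allows replacement after six or fewer doses, which covers subjects found at Days 3, 10 or 17 (1, 3 or 5 doses). With one replacement, a column of 6 has 7 subjects when the shift is found and 6 later. The later rows then show the planned number.

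**The case against.** Several stronger readings are tempting, and the documents do not support them.

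- *Anyone meeting the ASHA criteria is taken off drug.* Protocol 8.4.2 uses the criteria to trigger a review, and the AVDSMB decides on further dosing.
- *Discontinued subjects vanish from every later row.* No text says they skip the Day 10, 17 or 24 tests, and they are invited to EOS. A surveillance test entered under a nominal visit would be tabulated. SAP 4.4.4 keeps unscheduled laboratory results out of by-visit tables, but no such bar is written for audiometry. Absence is possible, not stated.
- *The events are lost.* Protocol 8.4.2 makes a test meeting the criteria an adverse event of interest. SAP 4.4.3 counts subjects with these events by dose, SAP 4.4.2 tabulates events leading to discontinuation, and the audiograms are listed. The affected subject also appears in the row where the shift is found.
- *Escalation is compromised.* The HFA escalation rule in Protocol 3.2 uses subject counts, not visit means.
- *It has already happened.* The protocol's document history reports one 2.5 mg/kg subject with a high-frequency change meeting ASHA criteria. It gives no arm, visit or discontinuation, so it is not evidence of dropout caused by hearing change.

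All of this limits the point, and the displayed n is a further cue. None of it repairs the summaries. The adverse-event tables carry no decibels, ear, frequency or persistence; listings do not correct a mean plot; and replacement can bring n back to the planned number.

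**Conclusion.** The point holds in a conditional form. SAP 4.4.6.2 has only by-visit, observed-case audiometry summaries, no assured row for surveillance audiograms, and no worst or ever-affected row to offset this. If a subject is discontinued after a hearing change and is not tested at the remaining on-treatment visits, means and ASHA percentages at Days 10-24 can fall with no recovery. For one subject the false fall is 3.3 to 6.7 dB in a column of 6 and 1.7 to 3.3 dB in a column of 12. This assumes a lasting shift of 20 to 40 dB and no change in the others; a 10 dB shift gives 1.7 or 0.8 dB. At EOS the effect depends on attendance. The defect is in the audiometry tables and plots, not in event capture, and a SAP change before the tables are produced is worth making.

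**What to change.** Add to SAP 4.4.6.2, by treatment and dose and separately by concentration, with placebo alongside:

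1. Number and percentage of subjects with ASHA significant change at any post-baseline test, for conventional and high frequencies separately, with confirmed (replicated) changes shown on their own line.
2. Worst post-baseline change for each ear and frequency.

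Both should use every audiogram in the database: scheduled, repeat, unscheduled and surveillance. The denominator is all Safety Population subjects with a baseline and at least one post-baseline test. Label early-termination EOS audiograms separately from scheduled EOS.

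I would not add a last-available-change row. Surveillance runs until resolution or permanence, so that row can itself show recovery.

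The cost is a few rows built on a method the SAP already uses for laboratory data, with no new testing. Two limits apply. Protocol 8.15 leaves some additional adverse-event follow-up outside the CRF, so late audiograms may not be available. Worst-value rows also absorb test-retest variability, which the document history reports for Cohort 1, and give retested subjects more chances of an extreme value. Read them against placebo and the confirmed-change count.

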4.4.6.3. Speech Reception Threshold

Speech reception threshold (SRT) will be performed at screening and baseline. At follow up visits, SRT will be performed only if there are ASHA significant change criteria/reverse ASHA significant change criteria noted in the PTA/HFA exam.

The number and percentage of responses (0-100, >100, no response, not done) will be summarized for each ear by visit, treatment and dose, and separately by concentration.

SRT response for each ear will be provided in by-subject data listings by cohort.

4.4.6.4. Tympanometry

The number and percentage of subjects with each type (A, As, Ad, B, C, not done) will be summarized for each ear by visit, treatment and dose and separately by concentration.

Tympanogram type for each ear and any abnormal tympanogram or other indication of middle ear abnormality will be provided in by-subject data listings by cohort.

4.4.6.5. Tinnitus Handicap Inventory Questionnaire

Tinnitus Handicap Inventory (THI) total score and change from baseline in THI total score will be summarized descriptively (n, mean, SD, median, min, max) at each visit by treatment and dose, and separately by concentration.

The number and percentage of subjects who have a score of a 5-point increase or greater in THI score from baseline accompanied by a shift in Grade (eg, from Grade 1 to Grade 2) as shown in the following table will be presented by treatment and dose, and separately by concentration.

Grade	Score	Description
1	0-16	Slight: Only heard in quiet environment, very easily masked. No interference with sleep or daily activities.
2	18-36	Mild: Easily masked by environmental sounds and easily forgotten with activities. May occasionally interfere with sleep but not daily activities.
3	38-56	Moderate: May be noticed, even in the presence of background or environmental noise, although daily activities may still be performed.
4	58-76	Severe: Almost always heard, rarely, if ever, masked. Leads to disturbed sleep pattern and can interfere with ability to carry out normal daily activities. Quiet activities affected adversely.
5	78-100	Catastrophic: Always heard, disturbed sleep patterns, difficulty with any activity.

Individual questions as well as total scores for the THI will be provided in by-subject data listings by cohort.

4.4.6.6. Dizziness Handicap Inventory Questionnaire

Dizziness Handicap Inventory (DHI) total score and change from baseline will be summarized descriptively (n, mean, SD, median, min, max) at each visit by treatment and dose, and separately by concentration.

The number and percentage of subjects who have a score of 31 or greater on the DHI, a 5-point increase or greater from baseline, and an associated shift to the following category (eg, from mild to moderate handicap) will be summarized by treatment and dose, and separately by concentration.

- 16-34 points (mild handicap)

- 36-52 points (moderate handicap)
- 54 + points (severe handicap)

Individual questions and total scores for the DHI will be provided in by-subject data listings by cohort.

4.4.7. Electrocardiogram

Actual values and change from baseline to each on-study evaluation will be summarized for the following ECG results, heart rate, PR, QRS, QT, QTcB, and QTcF intervals.

ECG data for each subject will be provided in by-subject data listings.

4.4.8. Renal Injury Biomarkers

Renal injury biomarkers include KIM-1 and clusterin in urine. Renal injury biomarkers will be normalized by urine creatinine and computed using the following definition:

Renal Injury Biomarker / Urine Creatinine.

Actual value and changes from baseline in each of the renal injury biomarkers normalized by urine creatinine will be summarized descriptively at each timepoint by treatment and dose, and separately by concentration.

Renal injury biomarkers, urine creatinine and normalized renal injury biomarkers for each subject at each timepoint will be provided in data listings by cohort.

4.4.9. Concomitant Medications

Concomitant medications will be coded using the WHO Drug Dictionary. Results will be tabulated by anatomic therapeutic class (ATC), PT, treatment and dose, and separately by concentration.

Concomitant medications will be tabulated, where any medications that were not discontinued prior to the first dose of study medication will be included.

The use of concomitant medications will be included in a by-subject data listing by cohort.

5. CHANGES TO PLANNED ANALYSES

The study secondary objective remains unchanged, but the wording has been clarified to be more precise from “to assess linearity between ascending SC doses and PK parameters” to “to assess dose proportionality of exposure parameters (C_{max} and AUC)”. Subsequently, it is clarified furthermore in [Section 4.3.2](#) that the dose proportionality will be assessed using a power model separately on Day 1 and Day 29, including the log-transformed PK parameters as dependent variables and the log-transformed dose as the fixed effect. The protocol specified fixed effects of day and dose*day are not required for the model that is performed separately on each individual day and therefore are excluded from the power model.

